7 PARTICIPANT DISCONTINUATION/WITHDRAWAL

7.1 Discontinuation/Withdrawal from the Study

Participants are free to withdraw from participation in the study at any time upon request. An investigator may discontinue or withdraw a participant from the study for the following reasons:

- Pregnancy
- Significant study protocol non-compliance
- If any clinical AE, laboratory abnormality, or other medical condition or situation occurs such that continued participation in the study would not be in the best interest of the participant
- If the participant meets an exclusion criterion (either newly developed or not previously recognized) that precludes further study participation

Participants may discontinue or withdraw from the study for termination of the study by the sponsor or the regulatory authority.

Note: If a participant tests positive for COVID-19 after administration, an AE should be reported and the decision to withdraw from the study should be made based on the AE situation.

For participants who withdraw early, the investigator must record the reason for early withdrawal on the eCRF and carefully complete the final visit record on the eCRF. At the time of discontinuing from the study, if possible, an early withdraw visit should be conducted. See the SoA (Table 1) for assessments to be collected at the time of discontinuation of study.

This study endeavours to ensure that sufficient participants receive the study drug. Participants who withdraw from the study after enrolment, but prior to receiving study drug may be automatically replaced. Participants who withdraw from study after dosing may be replaced at the discretion of sponsor and investigator.

7.2 Lost to Follow-up

A participant will be considered lost to follow-up if he or she repeatedly fails to return for scheduled visits and is unable to be contacted by the study site.

The following actions must be taken if a participant fails to return to the study site for a required study visit:

- The site will attempt to contact the participant and reschedule the missed visit and counsel the participant on the importance of maintaining the assigned visit schedule, and ascertain if the participant wishes to and/or should continue in the study.
- Before a participant is deemed lost to follow-up, the investigator or designee will make every effort to regain contact with the participant (where possible, 3 telephone calls, texts, emails, or local equivalent methods). These contact attempts should be documented in the participant's medical record or study file.
- If the participant continues to be unreachable, he or she will be considered to have withdrawn from the study with a primary reason of lost to follow-up.

8 STUDY ASSESSMENTS AND PROCEDURES

Study procedures and their timing are summarized in the SoA (Table 1).

8.1 General Procedures

8.1.1 Demographic data

Demographic data will include age or year of birth, gender, and race/ethnicity.

8.1.2 Height and weight

Height and weight will be measured at screening and baseline. BMI will be calculated in the formula: $BMI = \text{weight (kg)} / \text{height}^2 \text{ (m}^2\text{)}$.

The data of height and weight will be recorded in the eCRF.

8.1.3 Medical History and Prior Therapy

Medical history related to the inclusion and exclusion criteria, other medical history of clinically significant disease starting within 3 months before signing the ICF, surgery history, reproductive status (i.e., no childbearing potential or childbearing potential), and allergy history will be collected.

Prior therapy includes medications used by the participant within 28 days prior to the single dose of study drug.

8.2 Pharmacokinetics and Immunogenicity

Blood samples will be collected to characterize the PK profile and anti-drug antibody (ADA) of rhTPO. Blood sampling for PK and ADA will be collected at the timepoints specified in Table 2 and Table 3.

Samples may be further characterized to determine the titer and the presence of neutralizing antibodies (NAb) if positive for ADA.

Refer to Laboratory Manual for information on the collection, processing, and shipment of samples to the Central Laboratory.

8.3 Pharmacodynamics

Hematology test will be performed by the site, in which platelet count (PLT) will be used as an indicator of PD. Blood sampling for PD will be collected at the timepoints specified in Table 3.

8.4 Safety Assessments

Planned time points for all safety assessments are provided in the SoA (Table 1).

8.4.1 Vital Signs

Vital signs include systolic and diastolic blood pressure (mmHg), respiration rate (breaths/min), heart rate (bpm), and body temperature (°C). Blood pressure (BP) and heart rate will be measured after 5 minutes of rest in a supine position in a quiet setting without distractions (e.g., television, cell phones).

Vital signs normal ranges as below:

SBP: 90 mmHg - 140 mmHg

DBP: 40 mmHg - 90 mmHg

Heart rate: 40 - 100 bpm

Respiration Rate: 10 - 22 breaths/min

Temperature: 35.5 - 37.5°C

8.4.2 Physical Examinations

A complete physical examination will be performed and include assessments of the following; general appearance, respiratory, cardiovascular, abdomen, skin, head and neck (including ears, eyes, nose and throat), lymph nodes, thyroid, musculoskeletal (including spine and extremities), urogenital, dermatological, gastrointestinal, endocrine, hematologic/lymphatic, and

neurological systems.

8.4.3 Electrocardiograms

ECG parameters including PR Interval, QRS duration, QT Interval, RR Interval, Corrected QT Interval (Fridericia) (QTcF), and ECG mean heart rate.

$QTcF = QT / (RR^{0.33})$. QT is the QT interval, RR is the standardised heart rate value, obtained by dividing the heart rate by 60.

12-lead ECGs will be obtained after the participant has been rested in a supine position for at least 10 minutes in the absence of environmental distractions (e.g., television, cell phones). The investigator or designated physician will review the 12-lead ECGs. If a participant shows an abnormal ECG, the abnormality will be followed to resolution.

The original ECG traces (per local practice) must be stored in the participant's medical record as source data.

ECG normal ranges as below:

Heart rate: 40-100 bpm

PR Interval: ≥ 120 to ≤ 220 msec

QRSD: < 120 msec

QT: < 500 msec

QTcF ≤ 450 msec both genders

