All clinical laboratory parameters will be analyzed descriptively. Summary statistics for baseline, on-treatment, and change from baseline in laboratory, vital signs, and ECG parameters will be provided by treatment group in table format. Mean change from baseline over time will be plotted with the corresponding standard errors. Values of safety laboratory parameters and urinalysis outside the reference range will be flagged as H (above the reference range) or L (below the reference range) in the listings. A summary will be prepared by counting both the values out of reference range and the number of patients in whom one or more abnormalities occurred after treatment. Shift tables may be provided for the changes with respect to reference range for the following groups of parameters: hematology, clinical chemistry, and urinalysis. For all parameters, these shifts may be tabulated within each treatment and by visit, for the comparison before and after treatment.

Patients with abnormalities for vital signs, ECG, physical exams or clinical laboratory parameters will be tabulated and listed in different tables. Abnormality ranges will be defined for actual values and for changes from reference.

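### Protocol section 8.4.3 defines RR as heart rate/60, the reciprocal of the RR interval, so QTcF computed as written is wrong at every rate except 60 bpm

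*Protocol*

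**What the plan says.** Section 8.4.3 lists the ECG variables to be recorded: "ECG parameters including PR Interval, QRS duration, QT Interval, RR Interval", followed by QTcF, which it labels as the Fridericia correction, and mean heart rate. It gives the formula QTcF = QT/RR^0.33 and explains the RR term: "RR is the standardised heart rate value, obtained by dividing the heart rate by 60". The same section sets normal ranges, among them "Heart rate: 40-100 bpm", QT below 500 msec and "QTcF ≤ 450 msec both genders".

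These values are used elsewhere in the protocol. ECG is one of the secondary safety endpoints (Table 5). The 12-lead ECG is part of the medical evaluation behind inclusion criterion 4. Section 9.3.4 plans "Summary statistics for baseline, on-treatment, and change from baseline in laboratory, vital signs, and ECG parameters", together with tables and listings of participants with ECG abnormalities. No other section gives a different definition of RR.

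**The concern.** The section uses RR in two incompatible ways. In the list of variables it is an interval; in the formula it is a rate scaled by 60. Fridericia's correction divides QT by the cube root of the RR interval in seconds, which is 60/HR. HR/60 is the reciprocal of that.

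The direction of the error can be seen without any reference. QT shortens as the heart speeds up, so a correction has to raise QT at fast rates and lower it at slow ones. Dividing by a power of HR/60 does the opposite.

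If the formula is applied as written, three things follow:

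- The 450 msec limit is misapplied in both directions: some volunteers with slow rates are flagged falsely, and real prolongation at ordinary or fast rates goes unflagged.
- Any change in heart rate between baseline and a later visit appears as a change in QTcF.
- The study has one arm, so no concurrent control would show that such a shift is an artefact.

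**Working it through.** **Inputs from section 8.4.3:** the formula QT/RR^0.33, RR = HR/60 as stated, the normal heart-rate range 40-100 bpm, and the limits QTcF ≤ 450 msec and QT < 500 msec. **Assumption, not in the protocol:** an illustrative QT of 400 msec in the table, and a true QTcF of 410 msec in two examples. The protocol gives no QTcF result to reproduce.

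**Formulas**

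- As written: QT/(HR/60)^0.33
- Correct RR: QT/(60/HR)^0.33
- Ratio, written to correct: (60/HR)^0.33/(HR/60)^0.33 = (60/HR)^0.66

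The ratio does not depend on QT and equals 1 only at 60 bpm. It is 1.31 at 40 bpm, 1.13 at 50, 0.90 at 70, 0.83 at 80 and 0.71 at 100.

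**QTcF in msec for an assumed QT of 400 msec**

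| HR (bpm) | As written | Correct RR | Difference |
|---|---|---|---|
| 40 | 457.3 | 349.9 | +107.4 |
| 50 | 424.8 | 376.6 | +48.2 |
| 60 | 400.0 | 400.0 | 0 |
| 75 | 371.6 | 430.6 | -59.0 |
| 80 | 363.8 | 439.8 | -76.1 |
| 90 | 349.9 | 457.3 | -107.4 |
| 100 | 337.9 | 473.4 | -135.5 |

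Differences are taken before rounding. The classification against 450 msec reverses at 40 bpm (normal becomes abnormal) and at 90 and 100 bpm (abnormal becomes normal).

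**False flag at a slow rate.** A true QTcF of 410 msec at 50 bpm means QT = 410 × (60/50)^0.33 = 435 msec. As written this becomes 435/(50/60)^0.33 = 462 msec.

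**Missed prolongation at an ordinary rate.** At 70 bpm the written formula returns 450 msec when the true QTcF is 450/0.903 = 498 msec, so every true value from just above 450 up to 498 msec is reported as normal.

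**Spurious change from baseline.** With true QTcF constant at 410 msec, a rise from 60 to 70 bpm changes the written value from 410 to 410 × 0.903 = 370.3 msec, a change of -39.7 msec.

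**Where the limit stops working.** As written, exceeding 450 msec needs QT > 450 × (HR/60)^0.33. This threshold reaches 500 msec at HR = 60 × (500/450)^(1/0.33), about 83 bpm. Above that rate no QT below 500 msec can breach the QTcF limit, so the limit adds nothing to the raw QT limit.

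**Exponent.** Using 1/3 in place of 0.33 moves the correct value by less than 1 msec over 40-100 bpm, for QT from 360 to 420 msec. The rounding is harmless; the error lies in the definition of RR.

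**The case against.** The strongest point is that use of the formula is not established. The protocol does not say whether QTcF is calculated from this sentence or taken from the ECG machine. It names Fridericia, records the RR interval as its own variable and keeps the original traces as source data. Correct values may therefore be recorded anyway, or be recoverable, and the sentence may be a drafting or translation slip. This stands as a condition on the size of the harm: the errors apply to any QTcF computed as written. It does not rescue the text. Section 9 says the SAP is to be developed from the protocol and CRF, so a faithful derivation would carry the inversion forward.

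Other limits on the consequences are also fair:

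- No eligibility criterion names a QTcF cut-off; the ECG enters through the investigator's judgement under inclusion criterion 4.
- Not every slow-rate volunteer would be flagged. At 50 bpm the written value exceeds 450 msec only if the true QTcF exceeds about 399 msec (450/1.128).
- A physician reviews each ECG. The separate QT limit helps less than it seems: a true QTcF of 498 msec at 70 bpm corresponds to a QT of about 473 msec, which is below 500.
- The primary endpoint is PK, the analysis is descriptive, and the stopping rule in section 5.6 does not mention QTcF. The error cannot alter a primary result.

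**Conclusion.** The definition is wrong as written and must be corrected. Heart rate/60 is the reciprocal of the RR interval in seconds, and nothing elsewhere in the protocol puts it right. Because the protocol fixes the formula itself, this is not a detail left to the SAP.

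Across the protocol's own normal heart-rate range, a QTcF computed this way runs from 31% too high at 40 bpm to 29% too low at 100 bpm. These percentages rest on no assumed QT; the millisecond examples rest on the illustrative values stated with them. Whether any recorded or reported value is affected depends on where QTcF comes from, which the protocol leaves open. The output at risk is the trial's only heart-rate-corrected QT measure: its limit, its change-from-baseline summaries and its abnormality tables.

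**What to change.** In section 8.4.3, replace the definition of RR with: RR is the RR interval in seconds, equal to 60 divided by heart rate (or the measured RR interval in msec divided by 1000), and QTcF = QT/RR^(1/3). State whether QTcF is reported by the ECG device or derived. Confirm that the device setting, the eCRF derivation and the SAS programs all use this form, and re-derive any QTcF already calculated the other way, together with any flag that depended on it.

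The cost is one line of protocol text and a check of the derivation. There is no added measurement and no burden on participants.

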8.4.4 Clinical Safety Laboratory Tests

Blood and urine samples for determination of clinical chemistry, haematology, coagulation and urinalysis will be performed by local laboratory.

Plateletcrit and platelet distribution width are adjunctive pharmacodynamic parameters and they will not be reviewed as part of clinical safety laboratory results.

Participants will abstain from all food at least 8 h prior to any safety laboratory evaluations (minimum of 12 h for lipid profile at screening).

Samples will be taken at the visits indicated in the SoA (Table 1). Allow repeat once for safety laboratory assessment to confirm initial result and trending. Blood sample is required as soon as possible for hematology in the presence of venous thrombosis. Additional samples may be collected if clinically significantly abnormal at the discretion of the investigator. The date, time

of collection and results (values, units and reference ranges) will be recorded on the appropriate eCRF.

The following laboratory variables detailed in Table 7 will be measured.

Table 7 Laboratory Safety Variables

Hematology	Clinical chemistry	Coagulation	Urinalysis
White blood cell count with differential (both absolute count and percentage): 
 • Lymphocyte • Neutrophils • Monocytes • Eosinophil • Basophil Red blood cell count Hematocrit Hemoglobin Reticulocyte count Platelet count mean Platelet volume Plateletcrit Platelet distribution width	Total bilirubin Direct bilirubin Alanine aminotransferase Aspartate aminotransferase Total protein Albumin Lactate dehydrogenase Creatine kinase Troponin Gamma-glutamyl transpeptidase Alkaline phosphatase Renal function tests: 
 • Urea • Creatinine • Uric acid Lipids: 
 • Total cholesterol • Triglycerides Electrolytes: 
 • Potassium • Sodium • Chlorine Glucose	Prothrombin time International normalized ratio Partial thromboplastin time or activated partial thromboplastin time Fibrinogen D-dimer	Specific gravity PH Leukocytes Nitrite Protein Glucose Ketone bodies Urobilinogen Bilirubin Blood Leukocyte microscopy ^a Erythrocyte microscopy ^a

a. If there are any abnormalities considered clinically significant, the urine sample will be sent for microscopic examination.

8.4.5 Virology Test

Blood samples collected at screening will be analysed for the following:

- HBsAg, HBsAb, HBeAg, HBeAb, HBcAb
- HCV antibody (In the case of positive HCV antibody, the test of HCV RNA will be followed)
- HIV antibody
- Syphilis (treponema pallidum particle assay, TPPA)

Nasopharyngeal or oropharyngeal swab will be collected for Coronavirus Disease 2019 (COVID-19) RT-PCR test.

8.4.6 Serum or Urine Pregnancy Test

Pregnancy test on urine or blood sample will be performed for female participants of childbearing potential. Samples for pregnancy testing will also be performed by local laboratory.

The serum pregnancy test will be performed at the screening visit, and the urine pregnancy test will be performed on Day-1 and afterwards. A serum pregnancy test must be performed if the urine pregnancy test is positive or equivocal.

8.4.7 Drug Abuse and Alcohol Test

Breath test and urine drug test will be performed at screening. Urine drug test includes at minimum:

- Amphetamines (AMP)
- Methamphetamines (MET)
- Methadone (MTD)
- Barbiturates (BAR)
- Benzodiazepines (BZO)
- Cocaine (COC)
- Opiates (OPI)
- Methyl enedioxy methamphetamine (MDMA)
- Phencyclidine (PCP)
- Tetrahydrocannabinol (THC)

8.4.8 Injection site examination

Injection site examination will be performed at baseline (Day -1) to ensure injection site is suitable prior to dosing.

8.4.9 Injection site reaction

Injection site reaction (ISR) is a type of hypersensitivity reaction that may be immediate, although it usually appears within 24-48 hours after injection. ISR, by definition, includes the

following: erythema, induration, ecchymosis, pain, pruritus, paresthesia, warmth, hemorrhage, swelling, etc. at the injection site. ISR will be assessed based on the CTCAE severity scale.

8.5 Adverse Events and Serious Adverse Events

8.5.1 Definitions

8.5.1.1 Definition of adverse event

An adverse event (AE) is defined as any untoward medical occurrence in a patient or clinical investigation participant administered a pharmaceutical product and which does not necessarily have to have a causal relationship with this treatment.

An AE can therefore be any unfavorable and unintended sign (including an abnormal laboratory finding), symptom, or disease temporally associated with the use of a medicinal product, whether or not considered related to medicinal product.

8.5.1.2 Definition of Serious Adverse Event

A **serious adverse event** is defined as any untoward medical occurrence that at any dose:

- 1) Resulting in death.
- 2) Life-threatening*.
- 3) Results in persistent or significant disability/incapacity.
- 4) Requires hospitalization or prolonged hospitalization**.
- 5) Congenital abnormalities/birth defects.
- 6) Other important medical events***.

* The term "**life-threatening**" in the definition of "serious" refers to an event in which the patient was at risk of death at the time of the event; it does not refer to an event which hypothetically might have caused death if it was more severe**. **Hospitalization** means transfer to an inpatient unit or emergency ward (usually meaning at least overnight)/intensive care unit for observation or treatment.

The following are not considered hospitalization:

- 1) Detention in a doctor's office or outpatient observation room;
- 2) Treated only in the emergency room not admitted to the hospital;

- 3) Hospitalization for scheduled surgical or other therapeutic or investigative purposes immediately prior to entry into the study, such as elective surgical hospitalization and no worsening of underlying disease;
- 4) Program-mandated hospitalization (e.g., program-required procedures);
- 5) Hospitalization for diagnosis or treatment prior to use of the investigational drug;
- 6) Any hospitalization not related to an adverse event, e.g., cosmetic surgery, hospitalization for non-medical reasons (e.g., reimbursement, benefits, or convalescence).
- 7) Hospitalization or prolonged hospitalization due to social, or convenience or administrative reasons (such as annual physical examination, hospitalization for reimbursement reasons, etc.).

Note: If there is a pre-planned hospitalization prior to the start of the study, the investigator will need to document this in the medical record and eCRF.

***Medical or scientific judgment should be exercised in deciding whether SAE reporting is appropriate in other situations such as important medical events that may not be immediately life-threatening or result in death or hospitalization but may jeopardize the patient or may require medical or surgical intervention to prevent one of the other outcomes listed in the above definition. These events should usually be considered serious. Examples of such events include intensive treatment in an emergency room or at home for allergic bronchospasm, blood dyscrasias or convulsions that do not result in hospitalization, or development of drug dependency or drug abuse.

8.5.1.3 Definition of Suspected and Unexpected Serious Adverse Reactions

Suspected and Unexpected Serious Adverse Reaction (SUSAR) means a serious adverse event that meets both of the following conditions:

Relevant (Related)*: there is a reasonable likelihood of correlation between the adverse event and the investigational drug according to the investigator and/or according to the sponsor's evaluation;

Unexpected (Unexpected)**: the nature, severity, consequences, or frequency of the adverse event is inconsistent with the safety reference information in the single safety reference document for the product specified in the protocol (e.g., investigator's brochure or product insert/summary of product characteristics for a marketed product).

*: For the purposes of this protocol, “related” means “definitely related” , “probably

related” , or “possibly related” .

** : For the purposes of this protocol, the drug safety reference information (RSI) for assessing the anticipation of adverse events can be found in: the investigator's brochure for the investigational drug.

8.5.2 Monitoring and Follow-up

8.5.2.1 Monitoring

Adverse event monitoring time period: from the time of participant signing the ICF until the end of the last visit.

Adverse medical events occurring after the participant has signed the ICF and prior to the first dose are recorded in the eCRF as history/concomitant illnesses and are not recorded as AEs unless one of the following is met: injury/damage resulting from the operation of any clinical laboratory test (AEs related to study operating procedures); AEs resulting from discontinuation of medication related to the study protocol; AEs meet SAE severity criteria.

8.5.2.2 Follow-up

The investigator or his/her designee should follow all adverse events occurring during the study, with unrelated adverse events followed until the end of the final visit, and related AEs followed until the adverse event returns to normal or baseline or stabilizes, or the abnormality is deemed by the investigator to be not clinically significant, or is reasonably explained, or the participant is lost to follow-up or dies. All AEs in the study must be treated and documented. Any waivers must be approved by the sponsor's safety contact.

For related adverse events, the investigator should follow up until any of the following is achieved:

- Events resolved or stabilized;
- The event returns the baseline level, if a baseline value is available;
- The investigators conclude that the abnormalities are not clinically significant;
- Events can be attributed to drugs other than the investigational drug or to factors unrelated to the study behavior;
- When more information is unlikely to be available again (patient or healthcare professional refuses to provide more information, or there is evidence that the patient is still missing visits after best efforts have been made).

